10.16.7 Immunogenicity of Tisotumab Vedotin (HuMax-TF-ADC)

Blood samples will be drawn for central analysis of ADA (both total and neutralizing). Analysis of ADA will be done in batches of several samples.

10.16.8 Hepatitis B, C, HPV and Cytomegalovirus Serology

Serology parameters will be analyzed at the site in the Dose Escalation part of the trial, and at a central laboratory in the Cohort Expansion part of the trial.

A blood sample will be drawn at screening for assessment of HBsAg, anti-HBs and anti-HBc, hepatitis C as well as antibodies to cytomegalovirus (CMV) antigen and serology.

- For CMV, anti-IgG and IgM will be assessed and, in case of positive IgM, it will be confirmed with CMV polymerase chain reaction (PCR).
- For hepatitis C virus (HCV), anti-IgG will be assessed and, if positive, it will be confirmed with HCV PCR.

In patients with cervical cancer, the HPV status must also be available at screening.

Blood samples will be drawn for assessment of antibodies to CMV antigen after the end of trial drug administration (at the EOT Visit).

Final 5.0 (incorporating Protocol Amendment 4) 06 Jul 2017

10.17 Pharmacokinetic Assessments

Blood samples for assessment of tisotumab vedotin (HuMax-TF-ADC) and MMAE will be drawn for central analysis in accordance to the timing provided in Table 2 and Table 4 according to the initially designed treatment scheme, and in Table 6 after implementation of the urgent safety measure (Protocol Amendment 4.0). Two assays will be used for tisotumab vedotin (HuMax-TF-ADC), one detecting tisotumab vedotin (HuMax-TF-ADC) only and one detecting tisotumab vedotin (HuMax-TF-ADC) and non-conjugated Humax-TF.

10.18 Tumor Biopsy

A paraffin-embedded tumor tissue or cytology sample will be obtained at screening. This biopsy should be performed at least two weeks prior to dosing to ensure healing of wound.

An archived sample may be used as the screening sample. The most recent available archived sample should be used.

All biopsies will be analyzed retrospectively in a centralized CAP/CLIA (College of American Pathologists/Clinical Laboratory Improvement Act) certified laboratory.

10.19 Biomarkers

Plasma samples will be drawn for later central laboratory analysis of biomarkers. The samples will be collected at screening for both parts of the trial, but the second sample will be collected at the Day 15 visit of Cycle 5 in the Dose Escalation part and at the Day 15 visit of Cycle 4 in the Cohort Expansion part.

10.19.1 Circulating TF

An analytically validated assay, based on detection of TF using TF-specific antibodies, is being developed to measure total levels of circulating TF in plasma.

If the analysis method has not been qualified at the end of the trial, all patient samples will be destroyed.

10.19.2 Circulating cfDNA

Final 5.0 (incorporating Protocol Amendment 4) 06 Jul 2017

11 ASSESSMENT AND REPORTING OF ADVERSE EVENTS

11.1 Adverse Events Characterization

11.1.1 Definition of Adverse Events

An AE is any untoward medical occurrence in a patient administered a pharmaceutical product and which does not necessarily have a causal relationship with this treatment.

Adverse events include the following:

- All suspected adverse drug reactions.
- All reactions from medication overdose, abuse, withdrawal, sensitivity or toxicity.
- Apparently unrelated illnesses, including the worsening of a pre-existing illness.
- Injury or accidents. Note that if a medical condition is known to have caused the injury or accident, the medical condition and the accident should be reported as two separate AEs.
- Abnormalities in physiological testing or physical examination findings that require clinical intervention or further investigation.
- Any clinically significant laboratory abnormality suggesting a disease and/or organ toxicity
 and is of a severity that requires active management (i.e., changes of dose, discontinuation
 of drug, more frequent follow-up or a diagnostic investigation), unless they are associated
 with an already reported clinical event.

11.1.2 Definition of Infusion-Related Reaction

Infusion-related AEs are defined as any AEs occurring during infusion where the onset date and time of the event occurs within infusion time, i.e., within the following interval: infusion start date and time ≤ AE onset date and time ≤ infusion end time plus one day (24 hours) and coded by Medical Dictionary for Regulatory Activities (MedDRA) preferred term as "Arthralgia", "Asthenia", "Bronchospasm", "Chills", "Cough", "Hyperhidrosis", "Dizziness", "Pyrexia", "Fatigue", "Flushing", "Headache", "Hypertension", "Hypotension", "Infusion related reaction", "Lethargy", "Malaise", "Myalgia", "Nausea", "Pruritus", "Tachycardia", "Tumor pain", or by MedDRA High Level term as "Exfoliative conditions" or "Dyspneas", "Dyspnoeas", "Breathing abnormalities" or by MedDRA High Level Group Term as "Allergic conditions". In addition the event should be judged related to trial drug by the investigator (Section 11.3.4).

11.1.3 Trial Disease

Signs and symptoms, which according to the investigator are expected and well known consequences of the cancer type, both in intensity and frequency, including disease progression should not be reported as AEs or SAEs. Any unexpected change in intensity or frequency should be reported as AE (or SAE if applicable). However, if a patient dies due to disease progression within 30 days after the last dose of IMP, it should be reported as an AE/SAE as described in Section 8.1.1.6.

Final 5.0 (incorporating Protocol Amendment 4) 06 Jul 2017

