1 SYNOPSIS

NAME OF SPONSOR: Genmab A/S PROTOCOL No.: GEN702

NAME OF TRIAL TREATMENT: Tisotumab vedotin (HuMax®-TF-ADC)

TITLE OF TRIAL: Dose-escalating and cohort expansion safety trial of tissue factor specific antibody drug conjugate tisotumab vedotin (HuMax®-TF-ADC) in patients with locally advanced and/or metastatic solid tumors known to express tissue factor

TRIAL CENTERS: The Dose Escalation part of the trial is planned to be performed in a maximum of three sites in Denmark, the United Kingdom (UK) and the United States of America (USA). The Cohort Expansion part of the trial is planned to be performed in the ongoing countries and in Hungary and potentially Belgium.

TRIAL PERIOD: A Dose Escalation part will be followed by a Cohort Expansion part. The trial will be stopped when the last patient included in the Cohort Expansion part completes the trial or when the last ongoing patient has discontinued treatment and attended the Safety follow-up Visit, whichever occurs first.

PHASE OF
DEVELOPMENT:
Dose Escalation part:
Phase I
Cohort Expansion part:
Phase II

PLANNED TRIAL DATES: Enrollment period is planned to last approximately 21 months.

OBJECTIVES:

Primary Trial Objective: To establish the tolerability of HuMax® tissue factor antibody drug conjugate tisotumab vedotin [HuMax-TF-ADC]) dosed three times every four weeks (3q4wk) in a mixed population of patients with specified solid tumors.

Secondary Trial Objective(s):

- To determine the maximum tolerated dose (MTD) and the recommended dose for phase II trials (RP2D) with tisotumab vedotin (HuMax-TF-ADC) dosed 3q4wk.
- To establish the pharmacokinetic (PK) profile of tisotumab vedotin (HuMax-TF-ADC) dosed 3q4wk.
- To evaluate the anti-tumor activity of tisotumab vedotin (HuMax-TF-ADC) dosed 3q4wk in a mixed population of patients with specified solid tumors.

TRIAL DESIGN AND METHODOLOGY:

The trial is a safety trial of HuMax-TF-ADC dosed 3q4wk (Days 1, 8 and 15 of each 28-day cycle) in a mixed population of patients with solid tumors known to express tissue factor (TF) and where the use of systemically administered tubulin inhibitors is part of standard of care (SoC). The trial consists of two parts, an open-label, multicenter, phase I, Dose Escalation part, followed by an open-label phase II Cohort Expansion part.

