7.2.2 Secondary Endpoints

- Safety laboratory parameters (hematology, biochemistry, coagulation factors and flow cytometry)
- Skin disorders
- Bleeding events
- Neuropathy
- PK parameters (clearance, volume of distribution and AUC [AUC0-Clast and AUC0-∞], Cmax, time of Cmax [Tmax], pre-dose values, and half-life of tisotumab vedotin (HuMax-TF-ADC) and free toxin [MMAE])
- Immunogenicity of tisotumab vedotin (HuMax-TF-ADC) (human anti-human antibodies)
- Anti-tumor activity measured by tumor shrinkage (based on CT-scan evaluations), change in PSA and CA 125
- Objective Response (Complete Response [CR] or PR), Disease Control (CR, PR or SD), Progression-Free Survival (PFS) and Duration of Response (DoR)

Final 5.0 (incorporating Protocol Amendment 4) 06 Jul 2017

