8.3 Trial Population

The patient population in the Dose Escalation part will encompass patients with advanced (locally advanced and/or metastatic) cancer of the ovary, cervix, endometrium, bladder, prostate (CRPC), esophagus or lung (NSCLC) who have failed available standard treatments or who are not candidates for standard therapy.

The specific indications for the Cohort Expansion part will be decided once the RP2D has been determined. The inclusion and exclusion criteria for a reduced number of previous lines of treatment will be specified for all potential indications.

The Dose Escalation part of the trial is planned to be performed in a maximum of three sites in Denmark, UK and the USA. The Cohort Expansion part of the trial is planned to be performed in the ongoing countries and in Hungary and Belgium.

Thirty two to 44 patients are planned to be enrolled in the trial. Assuming an anticipated screen failure rate of 30%, 57 to 76 patients will be screened in total.

- In the Dose Escalation part: 12 to 24 patients are planned to be enrolled: three to six patients per dose level for three dose levels (plus a potential intermediate dose cohort).
- In the Cohort Expansion part: 20 to 30 patients are planned to be enrolled in two or three indication arms.

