10.11 Bleeding Assessments

Major bleeding is defined as any of the following conditions according to the International Society on Thrombosis and Haemostasis (Shulman and Kearon, 2005):

- Fatal bleeding; and/or
- Symptomatic bleeding in critical area organ, such as intracranial, intraocular, retroperitoneal, intra-articular or pericardial, or intramuscular with compartment syndrome; and/or
- Bleeding causing a drop in hemoglobin level of 20 g/L (1.24 mmol/L) or more, or bleeding leading to transfusion of two or more units of whole blood or red cells.

Minor bleeding includes:

• Cutaneous bleeding, nose bleeding, oral cavity bleeding, menorrhagia, spontaneous muscle hematomas without compartment syndrome, grade 1 and 2 hematuria, and excessive bleeding after minor injury.

Any bleeding AE shall also be recorded with a CTCAE grading.

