12.5 Statistical Analysis of Secondary Endpoints

12.5.1 Clinical Safety Data

Bleeding (major and minor), skin disorders and neuropathy will be summarized and listed separately. Abnormal findings in physical examination, body weight, ECG measurements and vital signs will be listed. Ophthalmological evaluation will be listed.

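### Section 11.1.3 makes no exception for bleeding, so tumour bleeds judged expected can drop out of the AE-based primary endpoint and expedited reporting

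*Protocol*

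**What the plan says.** Section 11.1.3 (Trial Disease) removes certain signs and symptoms from reporting, on the investigator's opinion: "expected and well known consequences of the cancer type, both in intensity and frequency, including disease progression should not be reported as AEs or SAEs". Two provisions limit this rule. First, "Any unexpected change in intensity or frequency should be reported as AE (or SAE if applicable". Second, "if a patient dies due to disease progression within 30 days after the last dose of IMP, it should be reported as an AE/SAE". Bleeding is not mentioned.

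Elsewhere bleeding has special standing:

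- The synopsis describes the product as "tissue factor specific antibody drug conjugate tisotumab vedotin".
- "Bleeding events" is a secondary endpoint in 7.2.2.
- Section 10.11 defines major and minor bleeding and adds: "Any bleeding AE shall also be recorded with a CTCAE grading".
- Section 12.5.1 plans that "Bleeding (major and minor), skin disorders and neuropathy will be summarized and listed separately".
- Table 5, the schedule now in force for the Cohort Expansion part, marks a bleeding assessment at screening, Day 1 of each cycle, Day 15 of Cycle 1, the End of Trial Visit and unscheduled visits.

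The primary endpoint (7.2.1) is the incidence of AEs, SAEs, infusion-related AEs, grade 3 or higher AEs and drug-related AEs. Cohort Expansion tables are reported by indication (12.3).

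**The concern.** The trial is open-label and has no control arm. Whether one bleed in a patient with a bleeding-prone tumour comes from the disease or the drug is therefore hard to judge case by case. The usual protection is to count every bleed and record attribution as a separate item. Section 11.1.3 works the other way round: attribution to the disease comes first, and it decides whether there is an AE record at all.

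Seven tumour types are eligible, bladder, cervix and endometrium among them, and the minor-bleeding list in 10.11 itself includes menorrhagia and low-grade hematuria. If some bleeds in these patients are set aside as normal for the cancer, the primary safety tables understate bleeding, and more so in some indication arms than in others. The sponsor would also not see those events in expedited reports.

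**Working it through.** The protocol gives no bleeding rate and no share of bleeds judged expected, so there is no planned figure to reproduce. The check is of the text, followed by an illustration on assumed values.

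**Do other provisions bring an expected bleed back?**

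1. *Unexpected change (11.1.3).* The yardstick is what is usual for the cancer type, not the patient's own baseline. A first on-treatment hematuria of ordinary severity in bladder cancer could pass as expected.
2. *Suspected drug reactions are AEs (11.1.1).* This helps only if the investigator suspects the drug.
3. *Worsening of a pre-existing condition is an AE (11.1.3.1).* This covers bleeding already noted at baseline that worsens. It does not clearly cover new bleeding from a known tumour.
4. *All AEs are reported whether or not related (11.2).* Section 11.1.3 acts before this rule, by keeping the event out of AE reporting.

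The gap is narrowed but not closed.

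**What depends on AE status?**

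- *Primary endpoint (7.2.1, 12.4).* It is defined on AEs. A patient with any other AE still counts in the overall AE row, so the loss would show mainly in the bleeding preferred terms and, for serious or severe bleeds, in the SAE and grade 3 or higher rows.
- *24-hour reporting (11.4.2.1).* It covers SAEs and non-serious grade 3 AEs. A bleed withheld under 11.1.3 does not reach the sponsor by this route, so the sponsor's own causality assessment (11.4.4) has nothing to work on.
- *Monitoring.* In the Cohort Expansion part the DMC has no preplanned meetings and convenes on new safety signals (11.7). The 30-day Safety Follow-up Visit assesses SAEs only (9.2.5).

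**Does the bleeding endpoint depend on AE status?** The protocol does not say. Section 10.12 states a separate form for skin, and 10.13 states a standard eCRF scheme for neuropathy. Section 10.11 states neither for bleeding, and asks for a CTCAE grade only for a bleeding AE. Section 12.5.1 does not name the source of its bleeding summary.

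**Illustration.** Let *n* be patients in an arm, *p* the true proportion who bleed, and *f* the share of those patients whose bleeding is withheld as expected. The expected recorded count is n × p × (1 − f), and the chance of recording none is (1 − p(1 − f))^n. Take n = 10, since 20/2 = 30/3 = 10 from the planned 20 to 30 patients in two or three arms. Both *p* and *f* are assumptions.

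| p | f = 0 | f = 25% | f = 50% | f = 75% |
|---|---|---|---|---|
| 20% | 2.0 (10.7%) | 1.5 (19.7%) | 1.0 (34.9%) | 0.5 (59.9%) |
| 40% | 4.0 (0.6%) | 3.0 (2.8%) | 2.0 (10.7%) | 1.0 (34.9%) |
| 60% | 6.0 (<0.1%) | 4.5 (0.3%) | 3.0 (2.8%) | 1.5 (19.7%) |

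Cells give the expected number of patients with a recorded bleeding AE and, in brackets, the chance of none. Example: 10 × 0.40 × (1 − 0.50) = 2.0, and (1 − 0.20)^10 = 10.7%. Two arms with the same true 40% but *f* of 0 and 50% would show about 4 and 2 patients of 10.

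**The case against.** The strongest reply is that the rule is narrow. It excludes only signs expected in both intensity and frequency, requires unexpected change to be reported, and leaves suspected drug reactions as AEs. Bleeding also has its own scheduled assessment. Screening gives a baseline, unscheduled visits can catch bleeds between cycles, and hematology and coagulation are tested at every Table 5 visit. The endpoint is worded as bleeding events, not bleeding AEs, and the major and minor definitions do not require AE status. Finally, counting all tumour bleeding in a single-arm trial would not isolate a drug effect either.

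Much of this stands. A reader might infer that the bleeding endpoint is shown to be undercounted; the documents do not show that. If the assessment records every bleed and feeds the summary, *f* is zero for that endpoint, and the source of a summary table may properly be set in the SAP, which is not at hand. Nor do the documents support the inference that the trial could not detect a bleeding effect.

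The reply does not reach the primary endpoint or expedited reporting. Both are defined on AEs, so a bleed withheld under 11.1.3 is missing from them whatever the assessment records. Contamination by disease bleeding is a fair worry, but the relationship field (11.3.4) separates it visibly, whereas withholding the event leaves nothing to separate.

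**Conclusion.** The point holds in limited form. Section 11.1.3 has no exception for bleeding, so bleeds judged expected for the cancer can be lost from the primary AE, SAE and grade 3 or higher incidences and from expedited reporting, to a degree that may differ by indication arm. The effect on the separate bleeding endpoint is unclear, not demonstrated.

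The size cannot be derived from the documents; the table above rests wholly on assumed rates. That bladder, cervical and endometrial tumours bleed is a clinical assumption, consistent with the bleeding types listed in 10.11.

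Two further inferences should not be drawn. One is that dose-limiting toxicity decisions are now at risk because major bleeding is in Table 7. Those criteria apply to the Dose Escalation part only, Table 1 marks a bleeding assessment at all seven Cycle 1 visits, and the RP2D has already been set, so a change now alters no such decision. The other is that ocular, skin and neuropathy events share the problem. Nothing in the documents shows this, and each has its own recording or reporting provisions (10.12, 10.13, 11.4.2.1).

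**What to change.** Add to 11.1.3: this exception does not apply to bleeding events, which are always reported as an AE or SAE with CTCAE grade, major or minor class and relationship to trial drug, whether or not they are expected for the cancer. Keep the exception for progression itself and for other disease signs.

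Add to 10.11 or 12.5.1: all bleeds found at the bleeding assessment count in the bleeding summary, whatever their attribution.

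This is a reporting rule and changes no treatment. It costs two protocol sentences, a matching line in the eCRF guidelines and a few more AE reports. The reported bleeding incidence will be slightly higher and will include some disease-related bleeding, which the relationship field lets the report show separately.

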11.1.3.1 Pre-existing Conditions

In this trial, a pre-existing condition (i.e., a disorder present before the AE reporting period started and noted on the medical history/physical examination form) should not be reported as an AE. If a pre-existing condition worsens during the treatment period the event should be reported as an AE.

11.1.4 Procedures

Diagnostic and therapeutic non-invasive and invasive procedures, such as surgery, should not be reported as AEs. A medical condition for which an unscheduled procedure was performed, should however be reported if it meets the definition of an AE. For example, an acute appendicitis should be reported as the AE and not the appendectomy.

11.2 Adverse Event Reporting

The investigator must report all directly observed AEs and all AEs spontaneously reported by the patient. A general type of question should be used similar to "Do you have any health problems?" or "Have you had any health problems since your last visit?"

The reporting period for non-serious AEs begins from the day of first treatment administration until the end of the Follow-up period. Serious adverse events should be reported from the time the patient signs informed consent and until the end of the Follow-up period or until Safety Follow-up Visit. Any non-serious AEs (signs, symptoms and diagnosis) occurring between screening and the day of first treatment administration should be recorded as medical history.

All AEs that occur in patients during the AE reporting period must be reported, whether or not the event is treatment-related.

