7.2 Trial Endpoints

7.2.1 Primary Endpoint

The primary endpoint is the evaluation of AEs: incidences of AEs, SAEs, infusion-related AEs, CTCAE grade \geq 3 AEs and AEs related to trial drug during the trial.

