Bleeding Assessment	X	X				X	X				X		X
Skin Assessment	X	X				X	X				X		X
Neuropathy Assessment	X	X				X	X				X		X
Ophthalmological Evaluation	X					X^{13}				X^{13}	X^{13}		X^{13}
Radionuclide Bone Scan ¹⁴	X						X						X^9
LABORATORY ASSESSME	CNTS ¹⁵												
Hematology	X	X	X	X	X	X	X	X	X	X	X		X^9
Biochemistry	X	X	X	X	X	X	X	X	X	X	X		X^9
Coagulation factors	X	X	X	X	X	X	X	X	X	X	X		X^9

Treatment Cycle	Screening			Cycle 1				Cycl	le 2-9		EOT ¹	Withdrawal Safety Follow-up ²	Unscheduled
Visit Number	0	1^3	2 ³	3^3	4	5	1^3	2 ³	3^3	4	-	-	1-X
Day/Week	≤ 21 days prior to Visit C1-V1	1d	8d	15d	18d	22d	1d	8d	15d	22d	-	30 days after last dosing	-
Visit window ⁴		-	±1d	±1d	-±1d	±1d	±3d	±1d	±1d	±1d	-	±14d	-
PSA ¹⁴	X	X					X				X		X^{10}
CA 125 ¹⁶	X	X					X				X		X^{10}
Flow Cytometry		X^{17}					X^{17}				X		X^{10}
Pregnancy Test	X	X					X				X		X^{10}
ADA (Immunogenicity)	X	X					X						X^{10}
Hepatitis B, C, CMV, HPV ¹⁸	X										X		X^{10}
PK Sampling ¹⁹	X	X	X	X	X	X	X	X	X				X^{10}
Tumor biopsy	X^{20}					·							X^{10}
Biomarker	X					·			X^{21}				

Abbreviations: ADA=anti-drug antibody; CMV=cytomegalovirus; CRPC=Castration-resistant prostate cancer; CT=computerized tomography; ECG=electrocardiogram; ECOG=Eastern Cooperative Oncology Group; EOT=End of Trial; HBc=Hepatitis B core; HBs=Hepatitis B surface; HBsAg=Hepatitis B surface antigen; HCV=hepatitis C virus; HPV= human papilloma virus; Ig=Immunoglobulin; PCR=polymerase chain reaction; PD=progressive disease; PK=pharmacokinetic; PSA=prostate specific antigen; SAE=serious adverse event

Footnotes to Trial Flowchart: Cohort Expansion Part

¹ If the patient shows PD, is to start new anti-cancer treatment or withdraws from trial due to another reason during treatment, the EOT Visit should be performed as soon as possible after decision of withdrawal.

² Only SAEs will be assessed.

³ The patient shall stay at hospital for at least 2 hours after the infusion and may be requested to stay longer at the discretion of the investigator.

⁴ The specified visit windows are in accordance with the previous visit. Visit 1 of Cycle 2 and onwards should be performed 7 days ± 3 days after Day 22 of the previous cycle.

⁵ Informed consent must be obtained before or at the Screening Visit window i.e., may be reasonably prior to the screening date.

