8.1.1.4 Follow-up Phase

Dose Escalation Part

Patients will attend four follow up visits (FU1 to FU4) at six weekly intervals (± 7 days).

If the patient withdraws from treatment and has not started new anti-cancer treatment, or if the patient completes all treatment cycles, the patient will be followed by the site every six weeks for a maximum of four visits or until other treatment is initiated, for a maximum of 24 weeks. Then, the patient will return for an End of Trial (EOT) Visit.

Cohort Expansion Part

No follow-up visits will be included in the Cohort Expansion part.

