8.1.1.5 End of Trial Visit (EOT)

Dose Escalation Part

If a patient completes all follow-up visits, the EOT Visit should be performed four weeks after the end of the Follow-up Visit 4 period.

In case of withdrawal from the trial, the EOT Visit will be performed as soon as possible. The EOT Visit will include most assessments performed at the Screening Visit, and response assessments.

Cohort Expansion Part

If the patient shows PD, is to start new anti-cancer treatment or withdraws from trial due to another reason during treatment, the EOT Visit should be performed as soon as possible after decision of withdrawal.

The EOT Visit will include most assessments performed at the Screening Visit, and response assessments.

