8.1.1.6 Safety Follow-up Visit

Dose Escalation Part

Patients who withdraw from the trial before Follow-up Visit 1 will return for a Safety Follow-up Visit 30 days after the last dose of IMP. In the Safety Follow-up Visit, only SAEs will be

Final 5.0 (incorporating Protocol Amendment 4) 06 Jul 2017

assessed. If the patient has died within the 30 days this should be entered as an AE in the eCRF and reported as an SAE.

Cohort Expansion Part

Patients who withdraw from the trial will return for a Safety Follow-up Visit 30 days after the last dose of IMP. In the Safety Follow-up Visit, only SAEs will be assessed. If the patient has died within the 30 days this should be entered as an AE in the eCRF and reported as an SAE.

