8.2 Trial Duration and End of Trial

The enrollment period is planned to last approximately 21 months.

The trial will be stopped when the last patient enrolled in the Cohort Expansion part completes the trial or when the last ongoing patient has discontinued treatment and attended the Safety Follow-up Visit, whichever occurs first.

The end of trial ("trial completion") is defined as the date of the last protocol-specified visit/assessment for the last patient in the trial or the date the trial is closed by the sponsor, whichever occurs first.

All materials or supplies provided by the sponsor will be returned to the sponsor or designee upon trial completion, as directed by the site monitor. The IEC/IRB will be notified when the trial has been completed.

Genmab A/S reserves the right to temporarily suspend or prematurely discontinue this trial either at a single site, multiple sites or at all sites at any time for reasons including, but not limited to, safety or ethical issues, inaccurate or incomplete data recording, noncompliance, or unsatisfactory enrollment with respect to quality or quantity.

If the trial is prematurely terminated or suspended, Genmab A/S (or its representative) will inform the investigators/institutions and the regulatory authority(ies) of the termination or suspension and the reason(s) for the termination or suspension, in accordance with applicable regulatory requirement(s). The IEC/IRB should also be informed and provided with reason(s) for the termination or suspension by the sponsor or by the investigator/institution, as specified by the applicable regulatory requirement(s). In addition, arrangements will be made for the return of all unused trial drug and other materials or supplies provided by the sponsor.

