8.3.4.4 Evaluations at Withdrawal from the Trial

When a patient withdraws from the trial, investigators should attempt to obtain information and perform an EOT Visit and a 30 day Safety Follow-up Visit. The EOT Visit should be performed as soon as possible and prior to initiation of new treatment and will include most assessments performed at the Screening Visit, and response assessments (Section 12.5.3).

In the Dose Escalation part of the trial, the Safety Follow-up Visit should only be performed if the patient withdraws before attending Follow-up Visit 1. Only SAEs will be assessed at the Safety Follow-up Visit. For patients considered as lost to follow-up, the investigator should make an effort (at least one phone call or one written message to the patient), and document his/her effort (date and summary of the phone call or copy of the written message in the source documents), to complete the final evaluation. All results of these evaluations and observations, together with a narrative description of the reason(s) for removing the patient, must be recorded in the source documents. The primary reason for withdrawal will be recorded in the eCRF on End of Trial page.

Final 5.0 (incorporating Protocol Amendment 4) 06 Jul 2017

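### In the Cohort Expansion part, Section 11.2 ends non-serious AE reporting at a Follow-up period that this part does not have, and the 30-day visit takes SAEs only

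*Protocol*

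**What the plan says.** Protocol Section 11.2 defines the non-serious window without distinguishing the two parts: "The reporting period for non-serious AEs begins from the day of first treatment administration until the end of the Follow-up period". The SAE window, in the sentence that follows, runs to the end of the Follow-up period or to the Safety Follow-up Visit, so the protocol treats these as two different things.

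For the Cohort Expansion part, Section 8.1.1.4 states: "No follow-up visits will be included in the Cohort Expansion part". Table 5, the schedule in force after the urgent safety measure, has no follow-up column.

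The visit 30 days after the last dose is limited in each place that describes it. Section 8.1.1.6 says "In the Safety Follow-up Visit, only SAEs will be assessed", and Section 9.2.5 says the same. Section 8.3.4.4 has "Only SAEs will be assessed at the Safety Follow-up Visit". Table 5 footnote 2 has "Only SAEs will be assessed".

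On EOT, Section 8.1.1.5 says that after progression, new anti-cancer treatment or another withdrawal, "the EOT Visit should be performed as soon as possible after decision of withdrawal". No interval from the last dose is given.

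The primary endpoint (Section 7.2.1) counts all AEs, SAEs, infusion-related AEs, grade 3 or higher AEs, and "AEs related to trial drug during the trial".

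**The concern.** AE incidence is the primary endpoint, and most of its components include non-serious events. A collection window belongs in the protocol: an analysis plan can choose which recorded events to count, but cannot recover events that nobody recorded.

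In the Cohort Expansion part the window ends at something that is not there. A site following the visit schedule would ask about non-serious AEs for the last time at EOT. Progression is itself a reason for leaving the trial (Section 8.3.4.2), so an early EOT is an ordinary route. A new non-serious event after that date, including a grade 3 or ocular one, has no scheduled collection. This is the part changed by an urgent safety measure for ocular toxicity, and the sponsor wants even non-serious grade 2 ocular AEs within 24 hours (Section 11.4.2.1). With no valid date in the text, sites may also close AE reporting at different times.

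**Working it through.** The plan gives no figure to reproduce here. The check is a cross-reading plus a count of days.

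**1. Does the Section 11.2 stop date exist?**
- Dose Escalation: 4 follow-up visits × 6 weeks = 24 weeks, which matches the 24-week maximum in Sections 8.1.1.4 and 9.1.3. Table 1 marks AEs at these visits. The rule works.
- Cohort Expansion: 0 follow-up visits, so no Follow-up period and no stop date.

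**2. Where does scheduled collection actually end?** The AE row of Table 5 is marked at screening; Cycle 1 Days 1, 8 and 15; Cycles 2 to 9 Days 1 and 15; EOT; the Withdrawal Safety Follow-up (SAEs only); and, optionally, unscheduled visits. EOT is the last scheduled visit that takes non-serious AEs.

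**3. Does other text supply a date?**
- Section 7.2.1 refers to the trial as a whole, and the stopping rule in Section 8.2 runs to the point "when the last ongoing patient has discontinued treatment and attended the Safety Follow-up Visit". This can be read to reach past EOT, but it sets no per-patient date.
- Section 10.9 has AEs assessed at every visit. That is a general sentence; the SAE-only restriction is specific.
- Section 11.5 covers follow-up of AEs already reported, not the onset window for new ones.
- Section 8.3.4.3 sends patients who stop treatment to follow-up visits, which repeats the mismatch.
- Section 11.4.3 refers to a procedures manual, which is not at hand and does not amend Section 11.2.

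**4. How many days can be uncovered?** Illustration only. Assumptions: q3wk dosing without a dose hold, and progression found at a scheduled scan.
- The next Day 1 falls 21 to 24 days after the last dose (21-day minimum in Section 8.1; +3 days in Table 5).
- The scan is 0 to 7 days before that Day 1 (Table 5 footnote 12).
- Days from last dose to scan: d = 21 − 7 = 14 up to d = 24 − 0 = 24.
- With x = days from scan to EOT, uncovered days = max(0, 30 − d − x).

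| x | d = 14 | d = 24 |
|---|---|---|
| 0 | 16 | 6 |
| 3 | 13 | 3 |
| 7 | 9 | 0 |
| 16 | 0 | 0 |

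Further delay shortens the gap. After an ocular dose hold at its limit (12 weeks × 7 = 84 days, Section 8.3.4.1) it is zero, because 84 > 30.

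**5. Is the existing visit enough as an anchor?** Its window is 30 ± 14 days, so day 16 to day 44. A day-16 visit leaves 30 − 16 = 14 days, so the cut-off has to be a date rather than a visit.

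**The case against.** The strongest reply is that Table 5 governs the Cohort Expansion visits and, with the consistent SAE-only wording, yields a workable rule: non-serious AEs to EOT, SAEs to about 30 days. Section 11.2 would then merely carry wording that fits Dose Escalation, and nothing in the protocol promises 30 days of non-serious collection. Part of this stands. There is a de facto stop at EOT, and the day counts measure distance from a 30-day window, not from a commitment in the text. But EOT is not what Section 11.2 states, and it has no fixed distance from the last dose, so writing it into Section 11.2 would settle the wording and keep the gap.

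A reader might infer that non-serious events after EOT are never collected. The documents do not support that. Section 11.2 requires spontaneously reported AEs to be recorded, Section 9 tells patients to call between visits, and Section 9.2.3 has AEs assessed at unscheduled visits. These routes are ad hoc and set no end date, but they capture some events. The procedures manual may also reduce variation between sites.

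A reader might also infer that 6 to 16 of 30 days means a matching loss of incidence. It does not: a patient who already had the event still counts.

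Lastly, Dose Escalation patients who leave before Follow-up Visit 1 also have only the SAE-only visit (Table 1 footnote 3). That may look like the same error, but a Follow-up period exists in that part and Section 11.2 is not contradicted there.

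**Conclusion.** The point holds in a limited form. For the Cohort Expansion part, the stop date stated for non-serious AEs refers to a period that does not exist, and the last scheduled collection falls at an EOT visit that can come soon after the last dose. Compared with collection to day 30, the effect runs one way: it can only lower the count of non-serious AEs, including grade 3 or higher and related ones. The size cannot be estimated from the documents. The range of about 6 to 16 days rests on q3wk dosing without a hold, progression at a scheduled scan and EOT on the scan day; it shrinks to zero as EOT moves to day 30 or beyond.

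SAEs keep their own window. Infusion-related AEs are bounded at 24 hours after the infusion (Section 11.1.2), and related grade 3 or higher events already ongoing are followed under Section 11.5. Analyses are descriptive, so no test is at risk. It should still be corrected, because it concerns the primary endpoint, costs little, and events missed cannot be recovered later.

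**What to change.** - In Section 11.2, state that in the Cohort Expansion part all AEs, serious and non-serious, are collected until 30 days after the last dose. Define the cut-off by date.
- Use the Safety Follow-up Visit for this, with a status check through day 30 when the visit falls earlier in its ±14-day window.
- State that the rule also covers patients who complete all nine cycles. Sections 8.1.1.6 and 9.2.5 write the visit only for patients who withdraw from the trial, so completers are not clearly included.
- Align Sections 8.1.1.6, 8.3.4.4 and 9.2.5 and Table 5 footnote 2, and reconcile Section 8.3.4.3 with Section 8.1.1.4.
- Flag events that start after new anti-cancer therapy, so that they can be shown separately.

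Giving Dose Escalation patients who leave before Follow-up Visit 1 the same 30-day minimum is an optional step for consistency; collection in follow-up for the others stays as it is.

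The cost is wording changes and opening the AE form at a visit already in the schedule, with no additional patients. It means slightly more data entry, an occasional status check, some events after new therapy to flag, and a 30-day contact for completers if none is now held.
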